#### ***11.4.5 Physical Examination***

A complete physical examination will be performed at the Screening 1 Visit and the Baseline/Day 1 Visit. A symptom-directed physical examination will be performed, as needed, at the Screening 2 Visit, at all On-treatment Visits, at the Early Discontinuation Visit within 48 hours of stopping study medication, and at the 4-Week Follow-up Visit. The complete physical examination will include (but not limited to) the following organ or body system assessments: skin; head, eyes, ears, nose, and throat; thyroid; lungs; cardiovascular; abdomen (liver and spleen); extremities; lymph nodes; and a brief neurological exam. Abbreviated symptom-directed physical examinations will target signs and symptoms; any abnormal findings that are reported as AEs will be recorded in the CRF.

#### ***11.4.6 Toxicity Management***

Clinical events and clinically significant laboratory abnormalities will be graded according NCI CTCAE version 4.03 (Appendix [20.2](#)).

[Redacted text block]

#### 11.4.6.4 Management of Subjects with Elevated ALP, ALT, AST or Bilirubin

If a subject is *asymptomatic* but experiences clinically significant elevations of liver transaminases or Bilirubin, subjects must repeat physical examination and laboratory evaluation within 48-72 hours for repeat testing and close monitoring, preferably at the clinical research site or alternately at a local laboratory.

[REDACTED]

- 1 [REDACTED]

- 2 [REDACTED]

- 3 [REDACTED]

For confirmed elevations of above parameters, the subject must interrupt study drug. Close monitoring of study subjects includes:

- 1 [REDACTED]

- 2 [REDACTED]

- 3 [REDACTED]

- 4 [REDACTED]

- 5 [REDACTED]

- 6 [REDACTED]

- 7 [REDACTED]

[REDACTED]

[REDACTED]

[REDACTED]

[REDACTED]

- 1 [REDACTED]

[REDACTED]

- [REDACTED]
- [REDACTED]
- [REDACTED]

[REDACTED]

[REDACTED]

**11.5 Biomarker Analysis**

Serum samples will be stored at the central lab for potential evaluation of biomarkers of interest at Baseline and at Weeks 12 and 24.

**11.6 Assessments of Medication Adherence**

Drug accountability through the assessment of pill counts will be performed by clinic staff at each on-treatment evaluation visit.

[REDACTED]

[REDACTED]

## 12.0 STATISTICS

### 12.1 Sample Size and Power

This is a single arm, open label, PoC study in 25 adult subjects with PSC; and for which each patient will serve as their own control when observing ALP relative to Baseline. With respect to a potential range of -20% for worsening to 80% for improvement in percent ALP change from Baseline to 24 weeks, a reasonably applicable standard deviation is 25%. Thus, 0.80 power would apply for the two-sided 95% confidence interval for mean percent change from Baseline to 24 weeks to have its lower limit exceed 15% if the true mean percent change from Baseline to 24 weeks is at least 30%. Also, for a dichotomous responder criterion such as either a 50% ALP decrease from Baseline to 24 weeks or an ALP decrease to 1.5xULN at 24 weeks, 0.80 power would apply for the two-sided 95% confidence interval to have its lower limit exceed 10% if the true responder percentage is at least 40%. Thus, in this sense, a sample size of 25 is sufficient to determine if there is a positive signal in ALP during CVC treatment.

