## 1.7 SCOPE OF PLAN

This statistical analysis plan (SAP) provides a more technical and detailed elaboration of the statistical analyses of the efficacy and safety data as outlined or specified in the final protocol of Study Protocol 652-205 (version dated 19 November 2015) and the most recent amendment (Version 3 dated [14 June 2016]). Specifications of tables, figures, and data listings are contained in a separate document.

This SAP will indicate the methods to be used to analyze the safety and efficacy data collected during the study and will supersede any statistical analyses specified in the protocol. The planned analyses identified in this SAP will be included in regulatory submissions and future manuscripts. Additional exploratory analyses, which are not defined in this SAP, will be labeled as such in any study report or regulatory submission.

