### 7.1 PRIMARY EFFICACY ENDPOINT

The primary endpoint for this study is the percent change from baseline through Week 24 in ALP.

The percent change from baseline will be calculated as follows:

$$ALP (\%) = \frac{(value\ at\ each\ visit - baseline\ value)}{baseline\ value} \times 100$$

[REDACTED]

[REDACTED]

If the normality and homogeneity of variance assumptions are significantly violated, then the baseline and percentage change from baseline parameters are first ranked separately, using the combined data from all visits. Tied values will receive the mean value (midranks) of the corresponding ranks. Then, the same mixed-

effect repeated measure model with ranked data will be used for the primary efficacy analyses.

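### Do the opposite sign conventions for ALP change, and the stated responder power of 0.80, undermine the planning criteria in protocol 12.1?

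*Protocol*

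**What the plan says.** Protocol 12.1 (Sample Size and Power) opens with "This is a single arm, open label, PoC study in 25 adult subjects with PSC" and then fixes a scale: "With respect to a potential range of -20% for worsening to 80% for improvement in percent ALP change from Baseline to 24 weeks", for which "a reasonably applicable standard deviation is 25" percent. On that scale a reduction in ALP is a positive number. The next sentence claims a power of 0.80 for the two-sided 95% interval around the average improvement "to have its lower limit exceed 15% if the true mean percent change from Baseline to 24 weeks is at least 30" percent. For a responder defined by a 50% fall in ALP or a fall to 1.5 times ULN, it claims 0.80 power for the two-sided 95% interval "to have its lower limit exceed 10% if the true responder percentage is at least 40" percent. The section concludes that 25 subjects are enough to detect a positive signal.

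SAP 7.1 (Primary Efficacy Endpoint) says "The percent change from baseline will be calculated as follows" and gives (visit value - baseline value) / baseline value x 100, so a reduction is a negative number. SAP 1.7 says that the SAP "will supersede any statistical analyses specified in the protocol". The readable part of SAP 1.4 gives the sample size of about 25 and repeats neither the 15% nor the 10% threshold.

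**The concern.** Two things look wrong when the documents are read together.

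The first is the sign. If the protocol's threshold is carried unchanged to the SAP's endpoint, the planned 30% improvement becomes -30%. A lower limit above +15% could then be reached only if ALP went up. The 15% and 10% thresholds are the only readable figures that give a size to a positive signal, so a threshold on the wrong scale would leave the direction and the limit to be settled after the results were known.

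The second is the responder power. With exact (Clopper-Pearson) limits, 7 responders of 25 are enough to put the lower limit above 10%. The chance of at least 7 when the true rate is 40% is 0.926, which is well above the stated 0.80 and suggests an arithmetic error.

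**Working it through.** **Inputs (all protocol 12.1).** n = 25; SD 25 points; two-sided 95% intervals; true mean improvement 30 against a bound of 15; true responder rate 0.40 against a bound of 0.10; stated power 0.80 for each. No interval method is named for the responder rate.

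**1. Mean criterion on the protocol's scale.**
Noncentrality = (30 - 15)/25 x sqrt(25) = 3.0.
- Noncentral t with 24 df: power 0.821.
- Normal approximation: Phi(3.0 - 1.96) = Phi(1.04) = 0.851.
- By noncentral t, n = 24 gives 0.804 and n = 23 gives 0.785, so 24 is the smallest n that reaches 0.80.

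The stated 0.80 with 25 subjects is therefore fair and slightly conservative.

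**2. The same criterion on the SAP's scale.**
Let y be the SAP percent change. The protocol's quantity is -y. Its mean is minus the mean of y, its SD is unchanged, and the lower limit for -y is minus the upper limit for y. Hence:
- lower limit for -y above 15 is the same event as upper limit for y below -15;
- with a true mean of -30 and SD 25, P(upper limit below -15) = 0.821, as in step 1;
- the literal mix, P(lower limit for y above +15) with a true mean of -30, is about 0.

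The last line is the alarming one. It arises only if the threshold is kept and the scale defined beside it is dropped.

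**3. Responder criterion, reproducing 0.80.**
Standard error = sqrt(0.40 x 0.60/25) = 0.0980.
- Normal approximation without correction: Phi(0.30/0.0980 - 1.96) = 0.865.
- With continuity correction 1/(2n) = 0.02: Phi((0.30 - 0.02)/0.0980 - 1.96) = 0.815.
- With continuity correction at n = 24: Phi((0.30 - 0.0208)/0.1000 - 1.96) = 0.797.

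With the correction, 25 is the smallest n that reaches 0.80, which matches the protocol's statement.

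**4. Responder criterion, exact binomial power at n = 25 and p = 0.40.**

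| Interval | Fewest responders with lower limit above 10% | Power |
|---|---|---|
| Wald with continuity correction | 8 (lower limit 11.7%) | 0.846 |
| Clopper-Pearson | 7 (12.1%; 9.4% at 6) | 0.926 |
| Plain Wald | 7 (10.4%) | 0.926 |
| Wilson | 6 (11.5%) | 0.971 |
| Agresti-Coull | 6 (11.2%) | 0.971 |
| Jeffreys | 6 (10.7%) | 0.971 |

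So 0.93 is right for two of these intervals and is not the single true value. Every method in steps 3 and 4 gives at least 0.80 at 25 subjects.

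**The case for a change.** The best case for a change is this. The SAP takes precedence over the protocol's analyses, its readable text does not restate the thresholds, and SAP 1.2 says the findings will determine whether further controlled studies are warranted. A single-arm, open-label study with that aim gains from a threshold fixed in advance on the scale that will be reported. The responder interval also matters at the margin: 6 of 25 passes with Wilson limits and fails with Clopper-Pearson, and 7 of 25 passes with both but fails with continuity-corrected Wald.

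Part of this stands. The two documents do use opposite signs, no readable sentence connects them, and the readable text names no interval for the responder rate. An editorial line on each would be harmless.

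The rest does not carry the point. Protocol 12.1 is a sample-size justification, not a decision rule. The SAP's precedence covers analyses, and a planning statement about power is not one, so precedence does not reverse its sign. Protocol 12.2 and SAP 3.1 describe the analysis as descriptive, and SAP 1.3 calls the main objective exploratory. No readable SAP output is compared with 15% or 10%, so the marginal responder counts decide nothing. Text is also blacked out directly after the formula in SAP 7.1 and after the responder endpoints in SAP 7.2. One cannot conclude that the criterion or the method is absent from the plan.

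**Conclusion.** The concern does not call for a change. The sign difference is one of notation between two documents. Protocol 12.1 states its convention where it sets the threshold, and an analyst who reads that paragraph will turn it into an upper limit below -15% on the SAP scale. The power is the same on either scale (0.82 by noncentral t at 25 subjects).

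The responder power of 0.80 is not an error. It is reproduced by a continuity-corrected normal approximation (0.815), and it understates the exact binomial power (0.85 to 0.97 across the intervals tried). Any discrepancy is therefore on the safe side, and 25 subjects remain sufficient on the protocol's inputs.

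This rests on those inputs as given (SD 25 points, true mean improvement 30%, true responder rate 40%), on 25 subjects with Week 24 data, and on the thresholds being used for planning only, as the readable text indicates. That the sponsor used the continuity correction is an inference from the match, since the protocol does not say.

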## 7.2 SECONDARY EFFICACY ENDPOINTS

Secondary efficacy endpoints include the following:

- The proportion of patients who achieve ALP normalization (ALP values outside of the central laboratory reference range at baseline, but within the central laboratory reference range at each visit according to the central laboratory reference ranges) at each visit, with secondary endpoint defined at Week 24
- The proportion of patients who achieve a decrease in ALP of  $<1.5 \times \text{ULN}$  at each visit with secondary endpoint defined at Week 24
- The proportion of patients who achieve a 50% decrease in ALP from baseline at each visit, with secondary endpoint defined at Week 24

[REDACTED]

[REDACTED]

[REDACTED]

[Redacted text block]

[Redacted text block]

■ [Redacted text block]

[Redacted text block]

■ [Redacted text block]

■ [Redacted text block]

■ [Redacted text block]

■ [Redacted text block]

■ [Redacted text block]

[Redacted text block]

[Redacted text block]

Statistical Analysis Plan

---

[REDACTED]

[REDACTED]

[REDACTED]

[REDACTED]

[REDACTED]

[REDACTED]

[REDACTED]

[REDACTED]

[REDACTED]

[REDACTED]

[REDACTED]

[REDACTED]

[REDACTED]

[REDACTED]

[REDACTED]

[REDACTED]

[REDACTED]

[REDACTED]

[REDACTED]

[REDACTED]

[REDACTED]

[REDACTED]

[REDACTED]

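### Does the 40% responder rate in the sample-size section contradict its planned mean ALP decrease of 30% with SD 25%?

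*Protocol*

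**What the plan says.** Protocol 12.1 (Sample Size and Power) describes the trial thus: "This is a single arm, open label, PoC study in 25 adult subjects with PSC". It counts improvement as positive and takes "a potential range of -20% for worsening to 80% for improvement in percent ALP change", from which "a reasonably applicable standard deviation is 25" percent.

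Two statements follow, each with power 0.80 for a two-sided 95% confidence interval:

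- **Mean:** the interval has its "lower limit exceed 15% if the true mean percent change from Baseline to 24 weeks is at least 30" percent.
- **Responders:** for a dichotomous criterion, the interval is "to have its lower limit exceed 10% if the true responder percentage is at least 40" percent. The criterion is introduced by way of example, as a 50% ALP decrease or a decrease to 1.5xULN at 24 weeks.

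The section concludes that "in this sense, a sample size of 25 is sufficient to determine if there is a positive signal in ALP during CVC treatment". It names neither the interval method for the proportion nor a distribution for percent change, and it gives no source for the 40%.

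SAP 7.2 lists the responder criteria as separate secondary endpoints. One of them is: "The proportion of patients who achieve a 50% decrease in ALP from baseline at each visit, with secondary endpoint defined at Week 24".

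**The concern.** The stated range of -20% to 80% is 30% plus or minus two SDs of 25%, so the paragraph seems to have one response distribution in mind, centred on 30%. Under it a 50% decrease lies 0.8 SD above the mean, and clearly fewer than 40% of subjects would get that far. The two statements would then describe drugs of different strength, although both are offered as support for the same 25 subjects.

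What would be at stake is interpretation. A drug with exactly the effect for which the mean criterion is powered would, with an exact interval, more often than not leave the lower limit for the 50%-decrease proportion at or below 10%. A reader who relied on the stated 0.80 could take that as evidence against activity when it was the expected result. SAP 1.2 says the findings will determine whether further controlled studies are warranted, so such a misreading could matter.

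**Working it through.** **Inputs, all from Protocol 12.1.** n = 25; SD 25; range -20 to 80; true mean 30 against a limit of 15; true responder rate 0.40 against a limit of 0.10; two-sided 95% intervals; stated power 0.80.

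**1. The plan's own figures.**

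- *Mean.* Noncentrality = (30 - 15) / (25/√25) = 3. Power from the noncentral t with 24 degrees of freedom is 0.821 (normal approximation 0.851). The stated 0.80 is met.
- *Responders at 40%.* The standard error is √(0.40 × 0.60 / 25) = 0.0980. With continuity correction 1/(2 × 25) = 0.02, power = Φ((0.30 - 0.02)/0.0980 - 1.96) = 0.815. Exactly: the Clopper-Pearson lower limit is 0.094 at 6/25 and 0.121 at 7/25, so at least 7 responders are needed and P(X ≥ 7 | 25, 0.40) = 0.926. Wilson needs at least 6, giving 0.971. The stated 0.80 is met by each of these methods.

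**2. Share with a 50% decrease if mean is 30 and SD is 25.** The documents do not state the shape, so it is an assumption. Power is for the lower limit to exceed 10%.

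| Assumed shape | Rate | Power, ≥7/25 (Clopper-Pearson or Wald) | Power, ≥6/25 (Wilson) |
|---|---|---|---|
| Normal: 1 - Φ((50 - 30)/25) = 1 - Φ(0.8) | 21.2% | 0.27 | 0.44 |
| Lognormal Week 24/Baseline ratio, mean 0.70, SD 0.25 | 21.2% | 0.27 | 0.44 |
| Beta(1.5, 1.5) on -20 to 80 (SD 25) | 25.2% | 0.45 | 0.63 |
| Ceiling for any symmetric unimodal shape | 26.9% | 0.53 | 0.70 |

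Under normality a 40% rate needs a mean decrease of 50 - 0.2533 × 25 = 43.7%. At mean 30 and SD 25, reaching 40% takes a sharply bimodal response: a two-group normal mixture gets to 41.6% with within-group SD 5, but only 31.7% with SD 10. Mean and SD alone, with no restriction on shape, allow up to 625/(625 + 400) = 61%.

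**3. The other example, a decrease to 1.5xULN.** From a Baseline of b × ULN the required decrease is 100 × (1 - 1.5/b). Under the same normal model:

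| Baseline (xULN) | Decrease needed | Rate |
|---|---|---|
| 2.0 | 25.0% | 57.9% |
| 2.36 | 36.4% | 39.8% |
| 2.5 | 40.0% | 34.5% |
| 3.0 | 50.0% | 21.2% |

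**4. Either criterion met.** Entry requires ALP of at least 1.5xULN (Protocol 8.2, criterion 5). Below 3xULN the 1.5xULN target is the easier one; above it, the 50% decrease is. The documents give no Baseline distribution, so the spreads here are assumptions.

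| Baseline spread evenly over | Rate | Exact power (≥7/25) |
|---|---|---|
| 1.5 to 3.5xULN | 41.7% | 0.95 |
| 1.5 to 4xULN | 37.6% | 0.89 |
| 1.5 to 6xULN | 30.3% | 0.67 |

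So 40% can sit with a 30% mean decrease for the 1.5xULN criterion or for an either/or criterion, but not for a stand-alone 50% decrease with a unimodal response.

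**5. Where the 10% limit is used.** In the readable text it appears only in Protocol 12.1. Protocol 12.2 and SAP 3.1 call for descriptive statistics, SAP 1.4 repeats no power claim, and SAP 1.7 says the SAP supersedes the protocol's analyses.

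**The case for a change.** The strongest case for a change is that the conclusion of 12.1 leans on both statements without telling the reader that, for the 50% decrease, they assume different drug effects. No common interval method restores 0.80 at the implied rate: even the symmetric unimodal ceiling gives 0.53 exact and 0.70 Wilson. The phrase *at least* does not help, because power is quoted at the minimum of each condition and the two minima disagree. Nor is the 50% decrease only an illustration, since SAP 7.2 makes it an endpoint of its own at Week 24. The remedy would cost two or three sentences.

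What stands is the mismatch itself, for a stand-alone 50% decrease and a unimodal response. What does not stand is the step from there to a fault in the plan. The 40% is offered as a condition, not as a consequence of mean 30 and SD 25, and the power at that condition is right. The criterion is an example with an alternative that can be compatible. The harm needs a reader who treats a lower limit of 10% or less as a failed test, and the visible text sets no such test. Part of the sample-size text in the synopsis is also blacked out, so the basis for 40% may be given there.

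**Conclusion.** No change is called for. Both power figures in Protocol 12.1 are met at n = 25 under the conditions stated: 0.82 for the mean and 0.815 to 0.971 for the responder rate, depending on method. They are separate scenarios. Read together they fail to match only for a stand-alone 50% decrease, where a unimodal response with mean 30% and SD 25% implies a rate of about 21% to 25% and power of about 0.27 to 0.45 (Clopper-Pearson or Wald) or 0.44 to 0.63 (Wilson). That rests on an assumed shape. It does not carry over to the 1.5xULN criterion or to an either/or criterion, where the answer depends on a Baseline ALP distribution that the documents do not give.

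An explanatory sentence in 12.1 would change no sample size, endpoint, model or reported result. The study is a descriptive proof of concept, the 50%-decrease proportion is already a secondary endpoint, and no visible decision rule turns on its lower limit. An analyst interpreting that proportion can keep in mind that 40% is a separate and more optimistic scenario for this criterion, and that a lower limit of 10% or less is not by itself evidence of no ALP effect.

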### 12.2 General Considerations

Descriptive statistical methods will be used to summarize the data from this study. Unless stated otherwise, the term “descriptive statistics” refers to number of subjects (n), mean, median, standard deviation (SD), minimum, and maximum (with quartiles, 10-th percentile, and 90-th percentile when useful) for continuous data and frequencies and percentages for categorical data.

#### 12.2.1 Analysis Populations

**Intention to Treat (ITT) Population:** The ITT population will include all subjects enrolled to receive treatment.

**Per Protocol (PP) Population:** The PP population will include all subjects who are enrolled, have no contraindicated concomitant medications, have adequate study medication compliance.

**Safety Population:** The safety population will include all subjects who received at least one dose of study drug. This population will be used for all safety analyses

#### 12.2.2 Handling of Missing Data

Data will be analyzed as recorded. There will be no imputations conducted for missing data. A summary of missing data will be included in the final statistical report

#### 12.2.3 Subject Replacement

If a subject discontinues from the study for reasons other than safety, a replacement subject will be considered and included in the study analysis.

### 12.3 Subject Disposition

Subject disposition will be presented for all subjects. The number of subjects who completed the study and discontinued from the study will be provided. The reasons for early discontinuation also will be presented.

## 12.4 Efficacy

### 12.4.1 Efficacy Endpoint

The primary efficacy endpoint for this study is the percent change from Baseline through Week 24 in serum alkaline phosphatase. [REDACTED]

### 12.4.2 Methods of Analysis for Primary and Secondary Efficacy Endpoints

Percent changes in ALP from Baseline will be summarized using descriptive statistics for the respective pre-treatment and on-treatment visits. [REDACTED]

## 12.5 Safety

### 12.5.1 Safety Endpoints

Safety endpoints include:

- Evaluation of the safety and tolerability through 24 weeks of treatment in adult PSC subjects
- Evaluation of AEs, clinical laboratory tests, physical exam and 12-lead ECG.

## ***12.5.2 Methods of Analysis for Safety Endpoints***

### **12.5.2.1 Adverse Events**

AEs will be tabulated by the MedDRA preferred term and system-organ classification. The occurrence of TEAEs will be summarized by treatment group using MedDRA preferred terms, system organ classifications, and severity (see Sections [11.4.1.3](#) and [11.4.1.4](#)).

All AEs will be listed for individual subjects showing both verbatim and preferred terms. Separate summaries of treatment-emergent SAEs and TEAEs related to study drug will be generated.

Any event reported on the CRF that occurs on or after the initiation of study drug is defined as treatment-emergent. Additionally, it is assumed that an AE that was reported to have started on Day 1 without an associated onset time may have occurred after the initiation of study drug. Hence, AEs occurring on Day 1 with no associated onset time are assumed to be treatment-emergent.

